## Date: 3/17/2012

## Overview:

Essential tremor is a chronic progressive condition that results in disability and decreasing quality of life. Deep Brain Stimulation of the ventral intermediate nucleus of the thalamus has been shown to improve tremor of the limb up to 90% and was FDA approved in 1997.

One of the challenges of programming is the time it takes to optimize the tremor control. The initial clinic visits can take some time and may require additional visits to further optimize. This can be a significant burden on the patient due to lost productivity, disability and financial impacts.

Programming DBS entails evaluating the degree of tremor control at each contact, of which there are four on each lead and asses for side effects. This data allows the neurologist to choose the nest contact to stimulate from. This process can be tedious and is hampered by variability in the tremor frequency and amplitude that is inherent in ET, but also that there is often lingering benefit from the placement of the electrode is surgery. This benefit arises from the swelling that occurs with the multiple electrodes that are passed into the brain in order to determine the optimal placement, this effect does resolve.

Current DBS technology allows only for 4 contacts on each lead, currently in development with multiple companies are 8 to 16 contact leads and leads that allow for the current to be directed away from areas of side effects and toward the area of best efficacy. This will allow for better patient outcomes, however programming these leads with our current standard of care is daunting and would be too time consuming to be done practically in a standard DBS programming session. An alternative method would need to be found.

In order to facilitate safer and more effective lead placement in the operating room a functional atlas was created. This atlas is based on both the side effects and efficacy of symptom control data that is obtained in the OR and then plotted in reference to known points on the patient's pre-operative MRI. This atlas has allowed for faster and safer surgical planning for our DBS patients. We would like to use this atlas to predict the optimal contact and settings to program the DBS to, allowing a faster response to programing.

## Methods:

Patients who have been approved for DBS of the VIM nucleus of the thalamus to treat essential tremor will be approached to participate in the study. They will undergo our standard of care DBS electrode implantation. 30 patients will be studied after they sign the consent form. They may exit the study at any time.

On the day of their initial programming, which takes place in one of two locations the Vanderbilt Neurosurgery clinic or the Vanderbilt Neurology clinic, the patient will undergo the standard of care post-op CT scan of the brain to establish the final lead position. They will then undergo the standard evaluation of the DBS electrode to determine the optimal contact and settings to control their tremor. This will be done on both side if the patient has undergone a bilateral implant.

At the same time another neurologist will evaluate the DBS lead placement within the Vanderbilt functional atlas. They will determine the ideal contact to stimulate from as well as he predicted DBS settings including voltage and pulse width.

Once the two contacts have been determined they will be programmed into the patient system by the unblended neurologist. In a random fashion the two programs will be labeled either group A or B. The patient will also be blinded to the nature of the programs. This should take about 20 minutes longer than our standard initial programming session of an hour.

For the first two weeks patients will use group A and then after 2 weeks they will change to group B. At the end of the first two weeks the patient will fill out the ADL section of the FTM (Fahn-Tolusa-Marsden tremor rating scale) to rate their tremor control over the past two weeks. The compliance with this will be noted by the percentage of use of each group.

After one month the patient will return to clinic to undergo a formal evaluation of both tremor settings. This evaluation will include formal tremor rating scales using the FTM. These ratings will be video recorded. These evaluations will be performed by a blinded neurologist. Once group B has been evaluated they will change back to group A and wait 1 hour to allow for optimal tremor control to occur.

At the end of the session the patient will choose which program they liked the best and will be allowed additional programming to improve their tremor control. This should take about 3 hours.

At any point during the study period the patient may opt out if they are unhappy with their tremor control, they will exit the study and opt to choose the group they like the best and can be seen in clinic for additional programming.

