## Analysis:

The primary outcome measure is the difference on the FTM scale per side, each side will evaluated with the following items of the FTM to allow limb specific response:

Items: 5, 6, 11 and 14, these will be compared with a t-test

The total FTM will also be compared with the t-test as a secondary outcome

If there are any adverse events or unanticipated risks occur they will first be reported to the PI and to the IRB if they are deemed as SAE or unexpected. The protocol will then be re-assessed and changed in order to avoid further events and to ensure patient safety.

All subject related data will be kept on a password protected computer and will be kept for at least 6 years after the study closes.

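### The two-week ADL form is named for group A only, each program's total FTM is left undefined, and the unspecified t-test makes no stated provision for the fixed A-then-B order

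*Combined protocol and SAP*

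**What the plan says.** The standard and atlas-based programs are assigned to labels by chance: "In a random fashion the two programs will be labeled either group A or B". Every patient then uses A for two weeks and B for the next two.

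The Methods name one ADL form: "At the end of the first two weeks the patient will fill out the ADL section of the FTM", with a two-week recall. The next sentence covers both periods ("The compliance with this will be noted by the percentage of use of each group"), but no second ADL form is named.

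At one month the patient will "undergo a formal evaluation of both tremor settings". On content, the text says "This evaluation will include formal tremor rating scales using the FTM"; it does not say whether this includes the ADL section for either setting. The ratings are made by a blinded neurologist, B first: "Once group B has been evaluated they will change back to group A and wait 1 hour".

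The Analysis section compares items 5, 6, 11 and 14 per side with a t-test as the primary outcome. It adds: "The total FTM will also be compared with the t-test as a secondary outcome". It does not give the type of t-test, the ADL source for each program's total, or any order or period factor.

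**The concern.** There are two linked gaps.

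**ADL source.** A total FTM needs an ADL component for each program, and the two should be obtained alike. As written, A has a patient-completed form with a two-week recall. B has no such form, only whatever the one-month FTM includes. If ADL is also rated for A at that visit, the rating describes daily life after one hour on the setting in clinic. Different choices give different totals from the same patients, and nothing fixes the choice before the data are seen. A two-week ADL rating for B that is not collected on time cannot be properly recovered later.

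**Order.** Group A is always the first period at home, always rated second in clinic, and always rated after one hour; B is always the reverse, after about two weeks. Any resulting A-versus-B difference enters the atlas-versus-standard differences with a sign that depends on the label. If the analysis ignores order, this adds variance. If the labels split unevenly, it also moves the estimate. The Overview gives one possible cause, a surgical benefit that wears off, but no time course. That could act on ADL (week 2 against week 4) but hardly on clinic ratings about an hour apart. The clinic ratings have their own fixed differences in order and exposure, and these reach the primary items too.

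**Working it through.** The plan gives 30 patients but no alpha, power, effect size or SD, so there is no figure of its own to reproduce. All figures below are illustrative.

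**1. Possible constructions of the total**

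| Reading | ADL for A | ADL for B | Consequence |
|---|---|---|---|
| Week-2 form for A, visit rating for B | Two-week recall, by patient | At visit; recall window and rater not stated | Workable, but not written down |
| Full FTM rated twice at the visit | After one hour on A | After about two weeks on B | Unlike exposure |
| Visit omits ADL | Week-2 form | None | Only a total without ADL compares alike, for up to 30 of 30 patients |

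**2. Assumed inputs for the power figures.** One paired difference per patient, n = 30, two-sided alpha 0.05, normal differences with SD 1, simple random labelling. By the noncentral t, 80% power needs a difference of 0.529 SD.

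**3. Dilution under the second reading.** Let s be the share of the true total difference lying in ADL (assumed 0.1 to 0.4) and r the share of B's answers repeated for A (assumed 0.5 to 1). The expected difference kept is 1 − s·r.
- Mild: 1 − 0.1 × 0.5 = 0.95.
- Severe: 1 − 0.4 × 1 = 0.60.

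Power also depends on the correlation rho between ADL and non-ADL differences. Their SDs are taken as proportional to their means, and the ADL SD shrinks with its mean.

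| Case | rho 0 | rho 0.5 | rho 1 |
|---|---|---|---|
| Mild | 76% | 78% | 80% |
| Severe | 52% | 69% | 80% |

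**4. Order effect.** Write D = delta + p·S + e. D is the atlas-minus-standard difference, S = +1 if atlas is labelled A and −1 otherwise, and p is the additive A-versus-B shift in SD units. The order-adjusted power does not depend on p. Averaged over random splits it is 78.5%, and at fixed splits it is 79.9% (15:15), 78.3% (18:12) and 75.1% (20:10).

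| p | Paired t-test without order | With order term |
|---|---|---|
| 0 | 80% | 78.5% |
| 0.25 | 77.5% | 78.5% |
| 0.5 | 71% | 78.5% |

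Averaged over splits, type I error is about 5% for both analyses and the mean bias is within 0.002 SD.

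**5. Uneven labels.** From Binomial(30, 0.5), a split of 18:12 or more uneven has probability 36%, and 20:10 or more uneven 9.9%. The shift of the unadjusted mean is p(n1 − n2)/30. At p = 0.5:
- 18:12: 0.5 × 6/30 = 0.10 SD, which is 0.10/0.529 = 19% of the detectable difference.
- 20:10: 0.5 × 10/30 = 0.167 SD, which is 31%. Type I error given this split is about 10% unadjusted and 5% adjusted.

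**6. Form of the adjusted test.** The A-minus-B difference is S·D. Its mean is p + delta when atlas is A and p − delta when atlas is B. The two label groups therefore differ by 2·delta, and p cancels. Testing the intercept in step 4 is the same as a two-sample t-test of A-minus-B differences between the label groups.

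**The case against.** The strongest reply is that the ADL gap has a natural reading. No clinic visit falls at week 2, so a form is added there. B's period runs up to the one-month visit, where the FTM is used, and the protocol treats ADL as a section of that scale. On this reading B's ADL is collected and nothing is lost. This is plausible, and a reader who inferred that B's ADL will be missing would go beyond the text. It remains true that the reading is not stated, that no two-week recall is specified for B, and that the ADL rating entering A's total is left open.

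Second, the Analysis section does not commit to a test that ignores order. A two-sample t-test between label groups is still a t-test and is the adjusted analysis. So the fair criticism is that the test is unspecified.

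Third, the order term is not free. With simple random labels it has slightly less power when there is no order effect, and the unadjusted test is as good or better up to about 0.2 SD. The clear gain needs an effect near 0.5 SD, which the documents neither give nor exclude. Uneven splits also presuppose simple randomisation, while the method of labelling is not described; an equal split gives no shift. These points limit the size of the concern. The term still gives protection at small cost.

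Fourth, the one-hour wait has a stated purpose, to let tremor control settle, and nothing in the documents shows it is too short for the clinic items. That stands. It does not help an ADL rating, which concerns daily activities.

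**Conclusion.** The point holds as a minor one. The ADL source for each program's total is not defined, a two-week form is named for A only, and the t-test is unspecified as to pairing and order. The ADL gap concerns the secondary total; the order gap concerns the primary items as well.

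A reader might infer that the fixed sequence favours one programming method. It does not: labels are random, so average bias is nil and type I error averaged over splits stays near 5%. The harm is lost precision, plus a shift in the single trial if labels happen to split unevenly and an order effect exists.

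The size is unknown. The ADL share, repeated answers, correlation, order effect and labelling scheme are all assumptions. The severe dilution range (52% to 80% power) includes no loss at all, and its low end needs the largest share, full repetition and zero correlation together, under one of three readings.

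**What to change.** 1. At the one-month visit, before the switch back to A, have the patient complete the same ADL form with the same two-week recall, about group B.
2. In the Analysis section, define each program's total FTM as its clinic rating plus the ADL form from its own two-week period. Do not use an ADL rating of A taken after the one-hour wait. Give the total without ADL as a sensitivity analysis, since it is formed alike for both programs at one visit.
3. For primary and secondary outcomes, analyse the within-patient atlas-minus-standard difference with label order (+1/−1) as a factor and test the intercept. This is equivalent to the two-sample t-test of A-minus-B differences between label groups. State that it assumes an additive order effect and no carryover.
4. Since "At any point during the study period the patient may opt out", report how many patients have both ADL forms and both clinic ratings.

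**Cost:** one short form at a visit already planned, a few sentences and one degree of freedom. If there is no order effect, the order term costs about 1.5 points of power under simple random labelling (80% to 78.5%), or about 0.1 point at a 15:15 split.

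**Remaining limits:** the two ADL forms still come from different weeks, and the clinic ratings still follow one hour on A against about two weeks on B. The order factor deals with these only if their effects are additive.

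### The label fixes rating order and recency of use, and the t-test has no sequence term: an optional, low-cost gain in precision, not a correction of bias

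*Combined protocol and SAP*

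**What the plan says.** All of this is in the combined protocol and SAP.

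- **Labelling (Methods).** "In a random fashion the two programs will be labeled either group A or B". No ratio, blocking or method is given.
- **Home use (Methods).** "For the first two weeks patients will use group A and then after 2 weeks they will change to group B". Both programs are therefore used at home for about two weeks, in the order A then B.
- **Clinic rating (Methods).** Both programs are rated at one month by a blinded neurologist, B first. Then: "Once group B has been evaluated they will change back to group A and wait 1 hour to allow for optimal tremor control to occur". No counterbalancing of the visit order is described.
- **Sample (Methods).** "30 patients will be studied after they sign the consent form". Patients may leave early: "At any point during the study period the patient may opt out if they are unhappy with their tremor control".
- **Analysis (Analysis).** "The primary outcome measure is the difference on the FTM scale per side"; of the four named items, "these will be compared with a t-test". Total FTM is tested the same way as a secondary outcome. Pairing is not stated, and neither test has a sequence, period or position term.

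**The concern.** Once a program has its label, everything about how it is rated follows. B is rated first while it is the program in current use. A is rated at least an hour later in the visit, shortly after a switch. The two programs differ in rating order and in recency of exposure, not in whether they were used.

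The plan's own reason for the wait implies that tremor control takes time to settle after a change of program, and the Overview describes tremor variability as inherent in the condition. A difference between first and second rating is therefore plausible, though nothing shows that it exists. If it does, it adds a shift to each patient's atlas-minus-standard difference, with a sign that depends on which program was labelled B. A t-test that ignores the label treats that shift as noise. What is at stake is power in a 30-patient study.

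**Working it through.** **Inputs from the documents:** n = 30; random labels; fixed rating order B then A; t-test without a sequence term. The plan gives no alpha, power, effect size or SD, so it has no figure to reproduce.

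**Assumptions, none in the documents:** one paired difference per patient; two-sided 5%; SD of the difference set to 1; true effect 0.53 SD (chosen because it gives about 80% power at n = 30); simple 1:1 labelling in the current plan; additive position effect e, in SDs of the difference.

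**Model.** D = τ + s·e + error, where D is atlas minus standard, τ is the true effect, and s is +1 or −1 according to which program is labelled B.

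**1. Bias.** With 1:1 random labels the expected value of s is 0, so D has expectation τ. A single trial can still be off by chance: an 18:12 split shifts the unadjusted estimate by (18 − 12)/30 × e = 0.2e. Simulated type I error of the plain test under simple labelling stayed at 0.048 to 0.051 across e from 0 to 1.

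**2. Plain paired t-test.** The expected variance of D is 1 + e². Power comes from the noncentral t with 29 df and noncentrality 0.53 × √30 / √(1 + e²) = 2.903 / √(1 + e²).

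| e | 1 + e² | Noncentrality | Power |
|---|---|---|---|
| 0 | 1.00 | 2.903 | 80.1% |
| 0.1 | 1.01 | 2.889 | 79.7% |
| 0.25 | 1.0625 | 2.816 | 77.7% |
| 0.5 | 1.25 | 2.596 | 70.9% |
| 1.0 | 2.00 | 2.053 | 51.0% |

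Simulation under simple labelling agreed to within about a point (70.4% at e = 0.5, 50.0% at e = 1.0).

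**3. Sequence factor.** The effect is the mean of the two sequence-specific means, so e cancels at any split. Its standard error is 0.5 × √(1/n₁ + 1/n₂), with n − 2 df.

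- 15:15: SE = 0.5 × √(2/15) = 0.1826, noncentrality 2.903, 28 df, power 80.0% at any e. The cost at e = 0 is 80.1 − 80.0 = 0.1 points; break-even with the plain test is at e of about 0.05.
- No blocking, averaged over Binomial(30, 0.5) splits: 78.6%. The cost at e = 0 is 80.1 − 78.6 = 1.5 points; break-even is at e of about 0.20.
- Three opt-outs unrelated to outcome, leaving 15:12: SE = 0.5 × √(1/15 + 1/12) = 0.1936, noncentrality 2.737, 25 df, power 74.9%, against 75.5% for the plain test with 27 patients at e = 0. The cost is about 0.6 points.

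**4. Blocking with the plain t-test.** At exactly 15:15 the position shifts cancel in the mean but still inflate the estimated variance, so the test becomes conservative. Simulated type I error is about 0.03 at e = 0.5 and 0.006 at e = 1.0. Power is about 73% and 50%, so blocking alone recovers little.

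**The case against.** The plan already does much to protect the comparison. Labels are random, patient and rater are blinded, both programs get about two weeks of home use, and the hour's wait is there to let the effect of A settle. No evidence is offered that a position effect exists. On the figures above, the loss is 0.4 points at e = 0.1 and 2.4 at e = 0.25. It becomes large only from e = 0.5 upward, where position matters about as much as, or more than, the assumed treatment effect of 0.53 SD. All the power figures rest on assumed inputs. That stands, and it makes this an optional refinement.

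A reader might infer more: that the fixed order favours one method, or that one hour is too short for A. The documents support neither. Either method can be B with a chance that the random labelling decides, and the adequacy of the hour is not shown either way. A reader might also infer that a sequence term is worthless without blocking. The figures say otherwise: it averages 78.6%, against about 71% for the plain test at e = 0.5 and 51% at e = 1.0.

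The more serious form of the recency concern is carryover, or speed of onset, that differs between the two methods. A sequence term would not repair it, and the documents give no basis for sizing it. Opt-outs prompted by poor tremor control may also be related to outcome, whereas the opt-out figure above assumes that they are not.

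**Conclusion.** The point holds as an optional, inexpensive efficiency improvement. Label determines rating position, and the planned test has no term to absorb a position effect. With 1:1 random labels, an additive effect causes no expected bias and leaves average type I error near 5%; it can only cost precision. At the assumed true effect of 0.53 SD with 30 completers, an effect of 0.5 SD would cost about 9 points of power, and one of 0.1 SD under half a point. The documents do not say where in that range, or outside it, the truth lies. The absence of expected bias itself rests on 1:1 labelling, which the plan does not state.

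**What to change.** If the team takes this up, the two changes belong together:

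1. Assign labels in permuted blocks to 15:15, and state the method.
2. Analyse one atlas-minus-standard difference per patient with label sequence as a factor. Take the effect as the mean of the two sequence-specific means, report the position effect with its confidence interval, and report the analysed split after opt-outs.

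Do not block and keep the plain t-test. If blocking is not possible, the sequence factor alone is still worthwhile when the position effect is expected to exceed about 0.2 SD.

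The cost is a label list and one degree of freedom, plus the small power losses at e = 0 worked out above, which grow as opt-outs make the split more uneven. The visit order and the wait are left as they are. The plan should state that the change does not correct carryover or onset speed that differs by method, or outcome-related opt-outs.

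The model needs one value per patient. How to combine two sides is a separate point to settle, because the outcome is defined per side and bilateral implants are allowed (Methods: "This will be done on both side if the patient has undergone a bilateral implant").

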## Analysis:

The primary outcome measure is the difference on the FTM scale per side, each side will evaluated with the following items of the FTM to allow limb specific response:

Items: 5, 6, 11 and 14, these will be compared with a t-test

The total FTM will also be compared with the t-test as a secondary outcome

If there are any adverse events or unanticipated risks occur they will first be reported to the PI and to the IRB if they are deemed as SAE or unexpected. The protocol will then be re-assessed and changed in order to avoid further events and to ensure patient safety.

All subject related data will be kept on a password protected computer and will be kept for at least 6 years after the study closes.

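### One patient can supply two sides to the primary t-test, and the plan neither accounts for this nor names a single primary test

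*Combined protocol and SAP*

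**What the plan says.** The statistical plan is a few lines under Analysis. The primary outcome is given as: "The primary outcome measure is the difference on the FTM scale per side, each side will evaluated with the following items". Then: "Items: 5, 6, 11 and 14, these will be compared with a t-test". The stated purpose of choosing these items is a limb-specific result. The secondary outcome is: "The total FTM will also be compared with the t-test as a secondary outcome".

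Methods supplies the design facts that bear on this:

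- Size: "30 patients will be studied after they sign the consent form".
- Sides: on programming each electrode, "This will be done on both side if the patient has undergone a bilateral implant".
- Both programs are rated in each patient: "After one month the patient will return to clinic to undergo a formal evaluation of both tremor settings".
- Randomisation: "In a random fashion the two programs will be labeled either group A or B".

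The documents do not state how many patients will be bilateral, how two sides from one patient enter the analysis, whether the four items form one score, the significance level, or in words that the t-test is paired.

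**The concern.** An outcome defined by side, with one or two sides per patient, leaves the unit of the primary test open. Two natural ways of carrying out the plan each carry a risk.

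- **Pool all sides in one t-test.** The number of observations then lies between 30 and 60, and the test assumes that they are independent. If a patient's two differences tend to move together, the standard error is too small and false positives exceed the nominal level.
- **Test left and right separately.** Each test has one value per patient, so clustering disappears. There are now two primary tests and no rule for what counts as success.

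The four items raise a similar question, since the plan does not say whether they are combined. At stake is whether a nominally significant result can be taken at its stated error rate, and whether the choice of analysis is fixed before the data are seen.

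The likely size of the between-side correlation is unclear. Overview speaks of "evaluating the degree of tremor control at each contact, of which there are four on each lead", so each side may respond in its own way, which would keep it low. What reads as one A/B labelling per patient, and one rating visit, may raise it.

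**Working it through.** The plan gives no alpha, power, effect size or standard deviation, so there is no figure of its own to reproduce.

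**Inputs.** From the documents: 30 patients, one or two sides each. Assumed: two-sided 5%, normal differences, 8, 15 or 30 bilateral patients, and correlation r between the two side-level differences (atlas minus standard) of one patient.

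**1. Sides pooled.** Let b be the number of bilateral patients, u = 30 − b, and N = u + 2b sides. The variance of the pooled mean is inflated by

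DE = [u + b(2 + 2r)] / N,

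and the true error of a nominal 5% test is roughly 2[1 − Φ(1.96/√DE)].

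- b = 8, r = 0.1: DE = (22 + 8 × 2.2)/38 = 1.042, error about 5.5%.
- b = 15, r = 0.5: DE = (15 + 15 × 3)/45 = 1.333, 1.96/√1.333 = 1.70, error about 9.0%.
- b = 30, r = 0.7: DE = (30 × 3.4)/60 = 1.70, 1.96/√1.70 = 1.50, error about 13.3%.

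Simulation of the pooled paired t-test (200,000 replicates per cell; repeat runs agree to about 0.2 points) gives:

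| Bilateral (sides) | r = 0.1 | 0.3 | 0.5 | 0.7 |
|---|---|---|---|---|
| 8 (38) | 5.5% | 6.4% | 7.4% | 8.6% |
| 15 (45) | 5.8% | 7.4% | 9.1% | 10.7% |
| 30 (60) | 6.1% | 8.5% | 11.0% | 13.6% |

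At r = 0, DE = 1 and the error is 5%; the same holds if b = 0. With 30 bilateral patients and r = 0.5, 60 sides carry the information of 60/1.5 = 40. A paired t-test on one mean difference per patient gives 4.9 to 5.1% throughout.

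**2. Left and right tested separately, either counts as success.** If independent: 1 − 0.95² = 9.75%. Simulated with all 30 bilateral: about 9.7% at r = 0, falling to about 8.4% at r = 0.7.

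**3. Four items tested one by one, any one counts as success.** If independent: 1 − 0.95⁴ = 18.5%. Simulated: about 13.2% at inter-item correlation 0.7 and 9.5% at 0.9. This applies only under an any-item rule, which the plan does not state.

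**4. Cost of the patient-mean test.** Take b = 15 and a pooled p of exactly 0.05 (critical t on 44 df = 2.015), with the mean difference unchanged.

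- r = 0: pooled SE = √(1/45) = 0.149; patient-mean SE = √(15 + 15 × 0.5)/30 = 0.158; ratio 1.06. Then 2.015/1.06 = 1.90 on 29 df, p about 0.067.
- r = 0.5: patient-mean SE = √(15 + 15 × 0.75)/30 = 0.171; ratio to the expected naive SE 1.15. Then 2.015/1.15 = 1.75 on 29 df, p about 0.09.

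Pooling is valid at r = 0, so the move from 0.05 to 0.067 there is lost efficiency (equal patient weights, fewer degrees of freedom). It does not correct a false positive.

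**The case against.** The strongest reply is that the plan never says sides are pooled. A limb-specific outcome fits separate left and right analyses at least as well, and then none of the pooled-side error rates applies. This stands. It moves the gap from clustering to two unranked primary tests but does not close it.

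A second reply is that every error rate rests on assumed values, and the documents give no reason to expect a correlation of 0.3 rather than 0.1. This also stands. At 0.1 the inflation is about one percentage point or less.

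Third, a reader might infer that an unpaired test is planned, because the word is missing. The documents do not support that: every patient uses and is rated under both programs, and the outcome is a difference. Stating the pairing and the alpha is a clarification. Pairing the programs within a side does not, however, remove correlation between two sides of one patient.

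Fourth, a reader might infer an 18.5% error rate from the four items. That needs item-by-item testing and success on any one item. The plan states neither, and speaks of one primary outcome measure.

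**Conclusion.** The gap is real and should be fixed before analysis. The plan allows two sides per patient, tests an outcome defined by side, and neither accounts for the clustering nor names one primary test. Under pooling, the excess error runs from nothing (no bilateral patients or zero correlation) to 13.6% against a nominal 5% (all bilateral, correlation 0.7). Inflation is small at correlation 0.1 and material from about 0.3. Under separate left and right tests it is about 8 to 10% if either side suffices.

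The omissions can be read directly from the text. Their size cannot: it rests on an assumed two-sided 5% level, normal differences, and bilateral shares and correlations that the documents do not give. It would go too far to say that the plan commits to pooling sides or that its error rate is known to be inflated.

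**What to change.** In the Analysis section:

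1. Confirm which of items 5, 6, 11 and 14 are scored for each side; the documents do not reproduce the scale.
2. Define one primary score per treated side from those items, and take the atlas-minus-standard difference within each side.
3. Make one primary paired comparison that accounts for two sides per patient, prespecified as one of the following:
   - a paired t-test on patient-mean differences, which is simple and weights patients equally; or
   - a side-level mixed model with a random patient effect and t-based inference, which keeps the side as the unit. It weights a bilateral patient 2/(1 + r) times a unilateral one, for example 1.82 at r = 0.1 and 1.33 at r = 0.5.
4. Report single items and left/right results as secondary, which keeps the limb-specific information.
5. As clarifications, state the two-sided alpha and that the test is paired.

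This takes a few sentences and needs no extra patients or data. The downside is a somewhat larger p-value than naive pooling would give, part of which is only lost efficiency if the between-side correlation is near zero.
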